13.2 Trial Specific SAE Reporting requirements

In addition to the SAE reporting requirements defined in Table 3, for the purposes of this trial, the following events will also be considered SAEs and must be captured on the SAE form and reported to the CTR with 24 hours of knowledge of the event:

• Toxicity reactions of CTCAE grades 3 and above to trial IMPs (see Section 11.6)

These events should also be completed in the participant's medical notes.

The following adverse events are reasonably anticipated to occur in this population during routine care and treatment and as such, for the purposes of this trial, the following events will **not** require immediate reporting as SAEs:

- AEs as a result of IMP of Common Terminology Criteria for Adverse Events (CTCAE) grades 1 and 2.
- Loss of patency of the artery in the trial leg of CTCAE grades 1 and 2.

As stated above, acute limb ischaemia, major lower limb amputation, myocardial infarction, ischaemic stroke, major bleeding and death (all-cause mortality) are composite primary outcomes of the trial and are recorded the CRF as part of data collection, therefore they are not subject to expedited reporting at any grade on an SAE form.

These should be recorded on the Primary Composite and Bleeding Outcomes CRFs within 24 hours of knowledge of the event.

All anticipated events should also be completed in the participant's medical notes (see Figure 2).

Pre-existing conditions should only be reported if they meet the definitions for an SAE and if the condition worsens by at least one CTCAE grade.

[figure not shown]

Figure 2. Adverse event reporting procedures flow diagram.

Serious events should be reported on specified forms within 24 hours of knowledge of the event.

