13 Pharmacovigilance

The PI at each site is responsible for ensuring that all site staff involved in this trial are familiar with the content of this section.

All serious adverse events (SAEs) must be reported immediately (and within 24 hours of knowledge of the event) by the PI at the participating site to the CTR PV and Safety Specialist unless the SAE is specified as not requiring immediate reporting (see section 13.2). This includes SAEs related to IMPs.

The trial population comprises mainly elderly, unwell participants. Acute limb ischaemia, major amputation, myocardial infarction, ischaemic stroke, major bleeding and death are common. As these are composite primary outcomes of the trial, they will be recorded on the Primary Composite and Bleeding Outcomes CRF as part of data collection within 24 hours of knowledge of the event, and therefore not subject to expedited reporting on an SAE form. See the Adverse event reporting procedures flow diagram (Figure 2 on page 44).

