13.1 Definitions

Table 3. Definitions of Adverse and Serious Adverse Events and Reactions

Term	Definition
Adverse Event (AE)	Any untoward medical occurrence in a participant or clinical trial participant administered a medicinal product and which is not necessarily caused by or related to that product
Adverse Reaction (AR)	Any untoward and unintended response in a clinical trial participant to an investigational medicinal product which is related to any dose administered to that participant
Serious Adverse Event (SAE)	Any adverse event that - Results in death Is life-threatening* Required hospitalisation or prolongation of existing hospitalisation** Results in persistent or significant disability or incapacity Consists of a congenital anomaly or birth defect Other medically important condition***
Serious Adverse Reactions (SARs)	Any SAE occurring in a clinical trial participant for which there is a reasonable possibility that it is related to the IMP at any dose administered.
Suspected Unexpected Serious Adverse Reactions (SUSARs)	A SAR, the nature and severity of which is not consistent with the Reference Safety Information (RSI) for the IMP.

- *Note: The term 'life-threatening' in the definition of serious refers to an event in which the trial participant was at risk of death at the time of the event or it is suspected that used or continued use of the product would result in the subjects death; it does not refer to an event which hypothetically might have caused death if it were more severe.
- ** Note: Hospitalisation is defined as an inpatient admission, regardless of the length of stay, even if the hospitalisation is a precautionary measure for continued observation. Pre-planned hospitalisation e.g. for pre-existing conditions which have not worsened, or elective procedures, does not constitute an SAE.
- *** Note: other events that may not result in death, are not life-threatening, or do not require hospitalisation, may be considered as an SAE when, based upon appropriate medical judgement, the event may jeopardise the participant and may require medical or surgical intervention to prevent one of the outcomes listed above.

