13.4 Expectedness

The CI (or another delegated appropriately qualified individual) will assess each SAR to assess expectedness.

The expectedness assessment should be made with reference to the current Reference Safety Information (RSI) for each IMP. Expectedness decisions must be based purely on whether the event is listed in the RSI; other factors such as the participant population and participant history should not be taken into account. Expectedness is not related to what is an anticipated event within a particular disease.

SARs which add significant information on the specificity or severity of a known, already documented adverse event constitute unexpected events. Fatal and life-threatening (LT) SARs should not be considered expected (unless explicitly stated in the RSI and approved by the NCA). For example, an event more specific or more severe than that described in the RSI is considered unexpected.

Any AEs causally related to the endovascular procedure are likely to occur during and immediately after the procedure before the patient starts the trial medication. However, loss of patency of the trial leg is an expected AE related to the endovascular procedure and a secondary outcome measure.

Anticipated treatment-related AEs of grade ≤2 are not subject to expedited reporting. These should be completed in the participant's notes and submitted to the CTR in the normal timeframes for CRFs.

Any AEs that are solely causally related to the endovascular procedure are not subject to expedited reporting. These should be completed in the participant's notes.

The table below lists the RSIs that should be referenced:

Table 6. Reference Safety Information

and of here one of the first that the							
IMP	RSI to be used for expectedness	Relevant section to be used for					
	assessment	expectedness assessment					
Clopidogrel	SmPC for Clopidogrel 75mg	Section 4.8 of SmPC					
	tablet to be used as RSI						
Aspirin	SmPC for Aspirin 75mg tablet to	Section 4.8 of SmPC					
	be used as RSI						
Rivaroxaban	SmPC for Rivaroxaban 2.5mg	Section 4.8 of SmPC					
	tablet to be used as RSI						

RSI on any CTR trial will be reviewed regularly according to CTR procedures.

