13.5 Reporting procedures

13.5.1 Participating site responsibilities

The PI (or delegated medically qualified doctor from the trial team) should sign and date the SAE CRF to acknowledge that they have performed the seriousness and causality assessments. Investigators should also report SAEs to their health boards or trust in accordance with local practice.

A completed SAE form for all events requiring immediate reporting should be submitted via fax or email to the CTR within 24 hours of knowledge of the event. A separate form must be used to report each event, irrespective of whether or not the events had the same date of onset.

The participant will be identified only by trial number, month or year of birth and initials. The participant's name (or any other personal identifier) should not be used in any correspondence. It is also required that sites respond to and clarify any queries raised on any reported SAEs and report any additional information as and when it becomes available through to the resolution of the event. Additionally, CTR/pharmaceutical companies may request additional information relating to any SAEs/SARs and the site should provide as much information as is available to them to resolve these queries.

Serious Adverse Event (SAE) email address:

[contact]
SAE [contact]

SAEs should be reported from the time of signature of informed consent, throughout the treatment period up to, and including the participant's final follow-up visit (12, 24 or 36-months) or 30 days after withdrawal from trial treatment (whichever is soonest). SARs (such as long-term side effects of trial treatment under investigation) should continue to be reported until the end of follow-up as defined in the protocol (page 44).

SAEs should be graded using the National Cancer Institute (NCI) CTCAE Version 5.0 (https://ctep.cancer.gov/protocoldevelopment/electronic_applications/docs/CTCAE_v5_Quick_Reference_5x7.pdf).

An SAE form should contain at least the minimum information:

- Full participant trial number
- An Adverse Event / Adverse Reaction
- IMP or trial intervention
- A completed assessment of the seriousness, and causality as performed by the PI (or another appropriately medically qualified doctor registered on the delegation log)

If any of these details are missing, the site will be contacted and the information must be provided by the site to the CTR within 24 hours.

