13.8 Safety reports

A list of all SARs (expected and unexpected) will be reported annually to the MHRA REC and trial sponsor in the form of a Development Safety Update Report (DSUR). This report must be submitted within 60 days of the anniversary of the MHRA CTA approval date.

The CTR will report a list of all SARs (expected and unexpected) and any other safety recommendations to all PIs annually throughout the trial. This frequency may be reviewed and amended as necessary. This reporting will be done via the Investigator safety report (ISR).

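### Section 13.2 exempts drug-related events from immediate SAE reporting by CTCAE grade, not seriousness, so a serious grade 1–2 reaction has no timely trigger for expectedness and SUSAR assessment

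*Protocol*

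**What the plan says.** The opening of section 13 requires SAEs to be reported within 24 hours, "unless the SAE is specified as not requiring immediate reporting (see section 13.2). This includes SAEs related to IMPs".

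Table 3 in section 13.1 defines an SAE by outcome: death, threat to life, hospitalisation, disability, congenital anomaly, or another medically important condition. Its note on hospitalisation is wide: "Hospitalisation is defined as an inpatient admission, regardless of the length of stay, even if the hospitalisation is a precautionary measure for continued observation". An SAE with a reasonable possibility of relation to the trial drug is a SAR.

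Section 13.2 adds drug toxicity of grade 3 or above to the SAE definition. It then lists events that will not "require immediate reporting as SAEs", on the ground that they are anticipated in this population. One of these is "AEs as a result of IMP of Common Terminology Criteria for Adverse Events (CTCAE) grades 1 and 2".

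Section 13.4 restates the exemption in different terms: "Anticipated treatment-related AEs of grade ≤2 are not subject to expedited reporting". It adds that these events are noted locally and sent to the trials unit at the usual CRF pace. The same section says "Expectedness is not related to what is an anticipated event within a particular disease", and requires the CI to assess every SAR for expectedness.

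Section 13.5.1 asks for an SAE form for events that require immediate reporting. It also says "SAEs should be graded using the National Cancer Institute (NCI) CTCAE Version 5.0" and that AEs are not recorded in this trial. Under 13.5.2, an SAE goes for expectedness assessment once the trials unit receives it. Under 13.6, the SUSAR periods of 7 and 15 days run from receipt there. Section 13.8 promises that "A list of all SARs (expected and unexpected) will be reported annually to the MHRA REC".

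**The concern.** Severity grade and seriousness are different scales. Grade describes how intense an event is; seriousness describes its outcome or what it required. An exemption keyed to grade can therefore take in events that the protocol itself calls serious.

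The reason given for the exemption, that the events are anticipated, is not the test for a SUSAR. Section 13.4 ties expectedness to listing in the reference safety information alone. A low-grade reaction absent from that information, with an overnight stay for observation, is a potential SUSAR however familiar such events are in this population.

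At stake is the timely regulatory assessment of serious drug reactions that are not trial outcomes. Outcome events such as major bleeding and death have their own 24-hour CRF route and are not part of this point.

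**Working it through.** No arithmetic applies. The check follows one case through the text: a grade 2 reaction judged possibly related to a trial drug, with a precautionary overnight admission, that is not a trial outcome event.

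1. **Is it serious?** Yes. Table 3 counts any inpatient admission, with no grade threshold. Section 13.5.1 applies CTCAE grades to events already classed as SAEs and sets no minimum grade.
2. **Is it a SAR?** Yes. Table 5 treats a possible relationship as a reasonable possibility of causation.
3. **Is it exempt from the 24-hour rule?** Yes, as written. The opening of section 13 subjects its own rule to 13.2 and says that drug-related SAEs are covered. The 13.2 bullet names drug-related events of this grade and does not say non-serious.
4. **Could the bullet mean only non-serious events?** Then it would exempt nothing. A non-serious AE never needs SAE reporting, and 13.5.1 already leaves such events to the medical notes. The bullet has practical effect only on low-grade events that meet Table 3.
5. **Is an SAE form triggered?** Not by 13.5.1, which ties the form to events needing immediate reporting. The PI's sign-off on seriousness and causality is on that form.
6. **What starts expectedness review and the SUSAR clock?** In 13.5.2 and 13.6, receipt at the trials unit. If nothing is sent promptly, neither starts promptly.

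Other passages give the same case different instructions:

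| Place | Instruction for this case |
|---|---|
| Section 13 opening with 13.2 | Exempt from immediate SAE reporting |
| Line printed with Figure 2 (13.2) | Serious events go on the designated forms within 24 hours |
| 13.4, first paragraph | CI assesses every SAR for expectedness |
| 13.4, exemption | If anticipated and grade 2 or below: notes, then the trials unit at CRF pace |
| 13.5.1, end | AEs are not recorded; non-serious events go in the medical notes |

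The last two rows conflict however the 13.4 exemption is read. If it covers only non-serious events, 13.4 sends to the trials unit what 13.5.1 says is not recorded. If it covers serious events too, it sends SARs at CRF pace while the Figure 2 line asks for 24 hours. The two exemptions also differ in scope: 13.4 covers anticipated events, whereas in 13.2 anticipation is only the stated reason for the list and does not limit the bullet.

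Table 2 has an ad hoc row for SAEs and SARs and no row for AEs, so it does not show the CRF on which an exempted reaction would travel.

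**The case against.** A reader might infer that such a reaction gets no SAE form, no expectedness review and no SUSAR clock at all. The document does not support that. Section 13.2 lifts only immediate reporting. Section 13.3 requires causality assessment of each SAE and 13.4 requires expectedness assessment of each SAR, neither with a grade limit. Section 13.4 sends anticipated low-grade events to the trials unit, though later. Section 13.5.2 has investigator reports of suspected SARs reviewed immediately, so an SAE form is not the only conceivable trigger. The line with Figure 2 asks for serious events within 24 hours. For the same reasons, it does not follow that these reactions drop out of the annual SAR list: a late report can still be listed.

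A reader might also infer that the two-drug arms would be under-reported relative to clopidogrel alone. The excess that the protocol describes for two-drug regimens is in bleeding. Bleeding leading to hospitalisation, intervention, an unscheduled visit or a change of therapy is already in the primary safety outcome. Complications from trial medications are a tertiary outcome assessed at each follow-up. For other reactions the document gives no basis for expecting a difference between arms.

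Figure 2 is not available here and may branch on seriousness first.

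All of this stands as a limit on the claim. It does not remove the conflict. The duty to assess every SAR comes with no prompt route for a SAR excused from the form, and the CRF route is contradicted by 13.5.1. The 24-hour line sits in the same section as the exemption it contradicts. A correct figure would still leave the text inconsistent with it, and a site following 13.2 literally would be compliant.

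**Conclusion.** The exemption is wrong as written. It uses severity grade where Table 3 uses seriousness, and the opening of section 13 carries it over to SAEs, including drug-related ones. A serious grade 1–2 reaction is therefore excused from the 24-hour SAE form, and its expectedness review and SUSAR clock are left without a timely trigger. This conflicts with the line printed with Figure 2 and with the duty in 13.4 to assess every SAR. The supported result is conflicting instructions with delay, and possible loss where a site relies on the medical notes alone.

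The size cannot be judged. The protocol gives no rate of drug reactions that are both serious and grade 1–2, and the number may be small. No difference between arms is shown. The conclusion rests on the text of section 13 and on the ordinary reading that the 13.2 bullet means what it says, without an implied restriction to non-serious events.

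**What to change.** In 13.2 and 13.4, limit the exemption to drug-related events of CTCAE grade 1–2 that meet no Table 3 seriousness criterion. State that any drug-related event meeting a Table 3 criterion is reported on the SAE form within 24 hours whatever its grade, with trial outcome events keeping their own CRF route.

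Then reconcile the opening of section 13 with 13.2, 13.4 and 13.5.1. In particular, settle whether non-serious low-grade reactions are sent to the trials unit (13.4) or left in the medical notes (13.5.1), and use one scope for the exemption in 13.2 and 13.4. Check that Figure 2 agrees.

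The cost is a wording amendment and a small number of extra SAE forms at sites. Treatment, sample size and analysis are unchanged.

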13.3 Causality

Causal relationship of serious adverse events and serious adverse drug reactions in this trial will be assessed for the following:

Table 4. Causal relationship assessment of adverse events

IMPs: Clopidogrel, Aspirin and Rivaroxaban

nIMPs: N/A

Procedures: Endovascular procedure

The PI (or another delegated medically qualified doctor from the trial team) and CI (or another medically qualified doctor from the TMG) will assess each SAE to determine the causal relationship according to the following categories:

Table 5. Definition of causal relationship with IMP

Relationship	Description	Reasonable possibility that the SAE may have been caused by the IMP?
Unrelated	There is no evidence of any causal relationship with the trial/intervention	No
Unlikely	There is little evidence to suggest there is a causal relationship with the trial/intervention (e.g. the event did not occur within a reasonable time after administration of the trial medication). There is another reasonable explanation for the event (e.g. the participant's clinical condition, other concomitant treatment).	No
Possible	There is some evidence to suggest a causal relationship with the trial/intervention (e.g. because the event occurs within a reasonable time after administration of the trial medication). However, the influence of other factors may have contributed to the event (e.g. the participant's clinical condition, and other concomitant treatments).	Yes
Probable	There is evidence to suggest a causal relationship and the influence of other factors is unlikely.	Yes
Definite	There is clear evidence to suggest a causal relationship and other possible contributing factors can be ruled out.	Yes

The causality assessment given by the PI (or delegate) cannot be downgraded by the CI (or delegate), and in the case of disagreement both opinions will be provided.

13.4 Expectedness

The CI (or another delegated appropriately qualified individual) will assess each SAR to assess expectedness.

The expectedness assessment should be made with reference to the current Reference Safety Information (RSI) for each IMP. Expectedness decisions must be based purely on whether the event is listed in the RSI; other factors such as the participant population and participant history should not be taken into account. Expectedness is not related to what is an anticipated event within a particular disease.

SARs which add significant information on the specificity or severity of a known, already documented adverse event constitute unexpected events. Fatal and life-threatening (LT) SARs should not be considered expected (unless explicitly stated in the RSI and approved by the NCA). For example, an event more specific or more severe than that described in the RSI is considered unexpected.

Any AEs causally related to the endovascular procedure are likely to occur during and immediately after the procedure before the patient starts the trial medication. However, loss of patency of the trial leg is an expected AE related to the endovascular procedure and a secondary outcome measure.

Anticipated treatment-related AEs of grade ≤2 are not subject to expedited reporting. These should be completed in the participant's notes and submitted to the CTR in the normal timeframes for CRFs.

Any AEs that are solely causally related to the endovascular procedure are not subject to expedited reporting. These should be completed in the participant's notes.

The table below lists the RSIs that should be referenced:

Table 6. Reference Safety Information

and of here one of the first that the							
IMP	RSI to be used for expectedness	Relevant section to be used for					
	assessment	expectedness assessment					
Clopidogrel	SmPC for Clopidogrel 75mg	Section 4.8 of SmPC					
	tablet to be used as RSI						
Aspirin	SmPC for Aspirin 75mg tablet to	Section 4.8 of SmPC					
	be used as RSI						
Rivaroxaban	SmPC for Rivaroxaban 2.5mg	Section 4.8 of SmPC					
	tablet to be used as RSI						

RSI on any CTR trial will be reviewed regularly according to CTR procedures.

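### Section 13.4 exempts events judged solely procedural from SAE reporting at any severity, which contradicts sections 13, 13.2, 13.3 and 13.5.1

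*Protocol*

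**What the plan says.** The opening of Protocol section 13 requires the site to report every SAE within 24 hours, "unless the SAE is specified as not requiring immediate reporting (see section 13.2". Section 13.2 is the only place it names for exceptions.

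Section 13.2 lists two exemptions: AEs of grades 1 and 2 resulting from the IMP, and "Loss of patency of the artery in the trial leg of CTCAE grades 1 and 2". It also sends the components of the primary composite and major bleeding to their own CRF within 24 hours. Of those events it says "therefore they are not subject to expedited reporting at any grade on an SAE form".

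Section 13.3 names the endovascular procedure in Table 4 as a cause to be assessed. It says that the PI and the CI, or their delegates, "will assess each SAE to determine the causal relationship according to the following categories".

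Section 13.4 says that "loss of patency of the trial leg is an expected AE related to the endovascular procedure". It then gives two exemptions. The first has a grade limit: "Anticipated treatment-related AEs of grade ≤2 are not subject to expedited reporting". Those events are still to be sent to the CTR on the normal CRF timetable. The second has no limit: "Any AEs that are solely causally related to the endovascular procedure are not subject to expedited reporting". Its only recording instruction is "These should be completed in the participant's notes".

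Section 13.5.1 opens the SAE reporting period at consent, and 13.5.2 sends an event to the CI once the CTR has received it. Section 11.4 lets the clinician start the IMP on any day from the procedure to day 10 and encourages an early start.

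**The concern.** Two sites that each follow the protocol could handle the same serious event differently. One would complete an SAE form and obtain two causality opinions, and the other would write in the notes. The events in question fall in the days after the procedure, when drug exposure may already have begun and the effects of the procedure and of the antithrombotic are hard to separate. If no form reaches the CTR, nobody outside the site can question the attribution. The SAE listings seen by the IDMC, and the assessments behind SUSAR reports and the DSUR, would then depend partly on which section a site had read.

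**Working it through.** The point concerns consistency between rules, so there is no arithmetic. The check follows one event through each section and then tests the readings that might remove the conflict.

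**The event.** A participant has had the first IMP dose. An event of grade 3 or above then meets the seriousness criteria in Table 3. It is not one of the events that 13.2 routes to the outcomes CRF. The site judges it solely due to the procedure.

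| Section | What happens to it |
|---|---|
| 13 | SAE form within 24 hours, unless 13.2 exempts it |
| 13.2 | Not exempt: there is no procedure item, and the patency item stops at grade 2 |
| 13.3 | PI and CI both assess causality, with the procedure as a listed cause |
| 13.5.1 | Within the reporting period, which began at consent |
| 13.4 | No expedited report; an entry in the notes only |

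The first four rows agree with each other, and the last contradicts them.

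**Loss of patency.** At grade 3 or above it lies outside the 13.2 exemption. Section 13.4 describes it as related to the procedure, with no grade limit. If the site judges it solely procedural, the 13.4 exemption applies. The two sections therefore give different grade rules for the same event.

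**Does AE here mean non-serious only?** Section 13.5.1 uses the term that way. However, Table 3 defines an SAE as a kind of adverse event, and non-serious events would need no exemption from expedited reporting. On this reading the sentence has no content.

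**Does expedited reporting mean reporting to the regulator?** Section 13.2 uses the phrase for reporting on an SAE form. Section 13.4 sends these events to the notes and, unlike its preceding paragraph, does not mention the CTR.

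**Can procedural events overlap with drug exposure?** Section 13.4 says only that such events are likely to come before trial medication starts. With the IMP allowed from the day of the procedure, overlap is possible.

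**An example.** Clinically relevant non-major bleeding belongs to the primary safety outcome in section 5.3, and an admission for it would meet Table 3. The 24-hour CRF route in 13 and 13.2 names only major bleeding. Such a bleed, if judged solely procedural, would be collected as an outcome at the next scheduled visit but under 13.4 would have no SAE form.

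**The case against.** The strongest reply is that little depends on the sentence. Death, major bleeding, myocardial infarction, ischaemic stroke, acute limb ischaemia and major amputation go to the outcomes CRF within 24 hours with no causality filter. Patency, reintervention and the other bleeding outcomes are collected at 2, 6, 12, 24 and 36 months. *Solely* is also a restrictive word: an event with a reasonable possibility of IMP causation is not solely procedural and remains a SAR. The line closing 13.2, that serious events go on specified forms within 24 hours, suggests a drafting lapse rather than a deliberate exemption. Figure 2 is not visible in the text reviewed and may settle the matter.

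Most of this stands and limits the size of the problem. It does not remove the conflict, because the written rules still disagree whatever the figure shows. Collection at a scheduled visit also does not replace an SAE form with causality assessed by both PI and CI. That the site alone decides what is solely procedural is an inference from the notes-only instruction; the protocol does not say so.

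A reader might go further in two ways that the documents do not support. One is to conclude that the sections disagree on every serious loss of patency, and to multiply person-years by an admission rate to get a count. The protocol gives no such rate. Section 13.4 calls loss of patency related to the procedure, not solely related. Such a count would also include events on which the sections agree. The other is to conclude that SAEs will be under-counted differently by arm. The trial is open-label, so attribution is made with the allocation known and a risk exists, but nothing in the protocol shows that it will happen.

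**Conclusion.** The contradiction is real and lies in the current text. Followed as written, 13.4 would leave a serious event on drug without an SAE form and without CI causality review, where 13, 13.2 and 13.3 require both.

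The affected group is serious events after the first IMP dose that are not routed to the outcomes CRF and are judged solely procedural. It is probably small, since 13.4 itself expects most procedural events before the IMP starts, and the documents give no figure. The primary effectiveness analysis and the major-bleeding part of the primary safety outcome do not depend on the exemption. What is at stake is the consistency of SAE and SAR reporting. The conclusion assumes that *AE* in the disputed sentence includes serious events, which is the only reading that gives the sentence a function.

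**What to change.** Reconcile 13, 13.2, 13.3, 13.4, 13.5.1 and Figure 2 so that one rule applies. Either limit the procedure exemption in 13.4 to non-serious events, or list any exemption for serious events explicitly in 13.2 and make it consistent with SAE reporting from consent in 13.5.1. An exemption simply for everything before the first dose would create a new conflict with 13.5.1 unless that section were changed too.

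Under either option, a serious event after the first IMP dose that is not captured on the outcomes CRF should go on the SAE form, with causality for both the procedure and the IMP assessed by the PI and the CI. State the same grade rule for loss of patency in 13.2 and 13.4; which rule to adopt is for the sponsor.

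The cost is a wording amendment and a few more SAE forms, with no change to the design, the sample size or the primary analysis.
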